Research Program

(Version number: 02 Version date: 2022-05-03)

Project name: Clinical efficacy and safety of real-world patients with refractory rheumatoid arthritis (D2TRA) treated with Abciap in combination with Janus kinase (JAK) inhibitors

Bidder: Zhejiang Provincial People's Hospital

Department: Rheumatology and Immunology

Principal Investigator: [name]

Investigator's statement and protocol signature page

As the principal person in charge of this research project, I will follow the Ethical Review of Biomedical Research Involving Human Beings (2016) of the Ministry of Health, the Declaration of Helsinki (2013) of the WMA and the International Ethical Guidelines for Human Biomedical Research (2002) of the CIOMS and the ethical principles of the GCP, using the protocol approved by the ethics committee under the guidance of the quality management specifications for drug clinical trials, and conducting the study in accordance with the requirements of this protocol to ensure the scientific validity of the study and to protect the health and rights of the subjects.

Name: _____

Signature: _____

Date: _____

Program Summary

Program Title	Clinical efficacy and safety of real-world patients with refractory rheumatoid arthritis (D2TRA) treated with abciap in combination with Janus kinase (JAK) inhibitors
Version number/version date	02/ 2022-05-03
Sponsors and Participating Units	Zhejiang Provincial People's Hospital
Principal Investigator	
Nature of Research	Clinical Studies
Purpose of the study	To observe the clinical efficacy and safety of Abciap combined with JAK inhibitor in the treatment of D2TRA patients
Sample size	90
Research Subjects	Patients with refractory rheumatoid arthritis

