Sei Muraoka et al. Abatacept is Efficacious in the Treatment of Older Patients with csDMARD-Refractory Rheumatoid Arthritis: A Prospective, Multicenter, Observational Study. This Japanese prospective, multicenter, observational study demonstrated that abciap is effective and safe in older RA patients with a history of csDMARDs-refractory disease. In both younger and older patients with csDMARDs-refractory RA, abciap was shown to be more effective than adding or switching to new csDMARDs.

Sae Ochi et al. Preferable outcome of Janus kinase inhibitors for a group of difficult-to-treat rheumatoid arthritis patients: from the FIRST Registry. This Japanese study compared the response to different classes of b/tsDMARDs in D2TRA and vD2TRA patients who were not responding to multiple b/tsDMARDs. The results suggest that JAK inhibitors are the preferred treatment option for this type of D2TRA.

(2) Subject selection basis

Patients diagnosed with refractory rheumatoid arthritis who meet the 2021 European League Against Rheumatism (EULAR) diagnostic criteria for refractory rheumatoid arthritis

4. Research Content

(1) Test population: patients with refractory rheumatoid arthritis

(2) Sample size: 90 D2TRA patients

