(3) Specific study: 90 D2TRA patients who were ineffective to conventional disease-modifying antirheumatic drugs and ineffective to treatment with 2 or more biological/targeted disease-modifying antirheumatic drugs and treated with Abacap combined with JAK inhibitors attending the outpatient and inpatient departments of Zhejiang Provincial People's Hospital from March 2022 to March 2024 were prospectively included as the observation group. Thirty patients with D2TRA treated with abciap alone in the outpatient and inpatient departments of Zhejiang Provincial People's Hospital from August 2020 to November 2021 were selected as the historical control group. There was no statistically significant difference between the observation group and the control group in terms of gender, age, disease duration, number of pressure pain in 28 joints, number of swelling in 28 joints, and DAS28 score ($P > 0.05$). Drugs were billed according to the maximum number of days of medical insurance (4 weeks), and changes in laboratory tests, number of pressure pains in 28 joints, number of swelling in 28 joints, and DAS28 score were observed in the Abciap combined with JAK inhibitor treatment group, and pre- and post-self comparisons were performed at 0, 4, 8, 12, 16, 20, and 24 weeks, along with changes in joint ultrasound and adverse effects. The changes in laboratory tests, number of pressure pains in 28 joints, number of swelling in 28 joints, and DAS28 scores were also retrospectively collected from the group treated with Abacap alone, and before and after self-comparison was performed at 0, 4, 8, 12, 16, 20, and 24 weeks, along with observation of changes in joint ultrasound and adverse effects. In addition, we observed the changes in laboratory tests, the number of pressure pains in 28 joints, the number of swelling in 28 joints, and the DAS28 score at 0, 4, 8, 12, 16, 20, and 24 weeks in the group treated with Abatacept combined with JAK inhibitor and the group treated with Abatacept alone, and compared them between the two groups for a statistically significant difference at $P < 0.05$. We also observed the changes in joint ultrasound and The changes of adverse reactions were also observed between the 2 groups.

5. Research Methodology:

Enrollment criteria (diagnostic criteria, inclusion criteria, exclusion criteria)

(1) Diagnostic criteria

The diagnostic criteria for D2TRA refer to the definition criteria proposed by EULAR 2021:

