No intervention factors were imposed on the study subjects in the study. Prospectively, 90 patients with D2TRA who were ineffective to conventional disease-modifying antirheumatic drugs and ineffective to treatment with 2 or more biological/targeted disease-modifying antirheumatic drugs and treated with Abacap combined with JAK inhibitors attending the outpatient and inpatient departments of Zhejiang Provincial People's Hospital from March 2022 to March 2024 were included as the observation group. Thirty patients with D2TRA treated with abciap alone in the outpatient and inpatient departments of Zhejiang Provincial People's Hospital from August 2020 to November 2021 were selected as the historical control group. There was no statistically significant difference between the observation group and the control group in terms of gender, age, disease duration, number of pressure pain in 28 joints, number of swelling in 28 joints, and DAS28 score ($P > 0.05$). The dosage was 125 mg per dose by subcutaneous injection once a week, and the dosage was 5 mg per dose by oral injection twice a day. The drug was billed according to the maximum number of days of medical insurance (4 weeks), and patients were observed for rheumatoid factor, anti-cyclic citrullinated peptide antibodies, immunoglobulins (IgG, IgA and IgM), C-reactive protein, blood sedimentation, white blood cells, platelets, ghrelin, glutamic aminotransferase, glutamic oxalacetic aminotransferase, globulin, creatinine, glomerular filtration rate, 28 joints at 4, 8, 12, 16, 20 and 24 weeks before and after drug administration number of pressure pain, number of swelling in 28 joints, joint ultrasound, change in DAS28-ESR score and adverse effects. To observe the changes in laboratory test indices, number of pressure pain in 28 joints, number of swelling in 28 joints, and DAS28 scores in the Abciap combined with JAK inhibitor treatment group, before and after self-comparison at 0, 4, 8, 12, 16, 20, and 24 weeks, as well as the changes in joint ultrasound and adverse effects. Also retrospectively collected the changes in laboratory test indices, number of pressure pain in 28 joints, number of swelling in 28 joints, and DAS28 score in the group treated with Abacap alone, and performed a before-and-after self-comparison at 0, 4, 8, 12, 16, 20, and 24 weeks, while observing the changes in joint ultrasound and adverse effects. In addition, we observed the changes in laboratory indices, the number of pressure pain in 28 joints, the number of swelling in 28 joints, and the DAS28 score between the Abciap and JAK inhibitor treatment groups at 0, 4, 8, 12, 16, 20, and 24 weeks, and compared them between the two groups. The changes in joint ultrasound and adverse effects between the two groups were also observed, so as to observe the clinical efficacy and safety of the Abciap combined with JAK inhibitor treatment group. $DAS28 \leq 2.6$ was defined as clinical remission, $2.6 < DAS28 \leq 3.2$ as low activity, $3.2 < DAS28 \leq 5.1$ as moderate activity, and $DAS28 > 5.1$ as high activity.

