including the Declaration of Helsinki ethical guidelines for human medical research and the relevant Chinese clinical research study norms and regulations. In the course of the study, if there is a need to revise this protocol, the revised protocol must be submitted to the Ethics Committee again for approval before implementation.

The Informed Consent Form for this study has been approved by the Medical Ethics Committee. If the Informed Consent Form is amended in writing, it will be sent to the Ethics Committee for approval to obtain the subject's consent again. Before the start of the study, the investigator provides patients with detailed information about the study, including the nature of the study, the purpose of the study, the possible benefits and risks, and the rights and obligations of the patients. The patient is fully informed and agrees, and signs the Informed Consent Form before the study can begin.

11. Statistical analysis plan

SPSS software was used for statistical analysis. Normality tests were performed using the Kolmogorov-Smirnov test, and measures conforming to a normal distribution were expressed as mean \pm standard deviation ($\bar{x} \pm s$), and comparisons between groups were made using the two independent samples t-test; measures not conforming to a normal distribution were described by median and interquartile spacing, i.e., median (25th percentile, 75th percentile) [M(P25,P75)], and comparisons between groups were made using the Mann-Whitney U anecdotal test Comparisons between groups were made using the Mann-Whitney U anecdotal sum test; count data were expressed as percentages, and comparisons between groups were analyzed using the chi-square test or Fisher's exact probability method, with differences considered statistically significant at $P < 0.05$.

12、 Form of publication of research results

Published 1-2 papers

13.Data Logging Form

Observed indicators		Week 0	Week 4	Week 8	Week 12	Week 16	Week 20	Week 24
Rheumatoid factor	IU/ml							
Anti-cyclic citrulli	U/ml							

nated peptide antibody								
Immunoglobulin G	g/L							
Immunoglobulin A	g/L							
Immunoglobulin M	g/L							
C-reactive protein	mg/L							
Blood sedimentation	mm/h							
Leukocytes	$\times 10^9/L$							
Blood platelets	$\times 10^9/L$							
Glutathione aminotransferase	U/L							
Glutathione transa	U/L							

minase								
Globulin	g/L							
Creatinine	umol/L							
Glomerular filtration rate	ml/min							

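### Adverse effects are recorded prospectively in the combination group but can only be gathered retrospectively in the historical controls, so a between-group difference in total rates may reflect recording rather than treatment, in an undetermined direction

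*Protocol*

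**What the plan says.** **Combination group.** Section 4 fixes the size ("2) Sample size: 90 D2TRA patients") and the mode of inclusion ("from March 2022 to March 2024 were prospectively included as the observation group"). Section 7 schedules observation every four weeks to week 24, and Section 14 supplies an adverse reaction record form with onset, severity, causality, outcome and withdrawal.

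**Control group.** The controls are "Thirty patients with D2TRA treated with abciap alone in the outpatient and inpatient departments of Zhejiang Provincial People's Hospital from August 2020 to November 2021", described as historical. Enrolment of the combination group starts after that period, and the protocol itself is later still ("Version number: 02 Version date: 2022-05-03"). Section 7 describes the control data thus: "Also retrospectively collected the changes in laboratory test indices". The same sentence goes on to joint counts and DAS28 at weeks 0 to 24 and ends "while observing the changes in joint ultrasound and adverse effects".

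**Comparison.** Section 7 then says "The changes in joint ultrasound and adverse effects between the two groups were also observed", with the stated purpose of judging the efficacy and safety of the combination. Safety is one of the two aims in Section 1. For count data, Section 11 says "comparisons between groups were analyzed using the chi-square test or Fisher's exact probability method", at P < 0.05.

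**Two further rules bear on what is counted.** Section 9(2) reports only events related to the study drug, on a spontaneous report form. Exclusion criterion 4 in Section 5 removes patients who cannot adhere to the combination, or who have serious adverse reactions and do not complete the observation course.

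**The concern.** An adverse-effect rate is the product of how often events happen and how often they are recorded. Here the second factor is likely to differ by group. One group has scheduled visits and a dedicated form. The other was treated before the study, with no stated source or procedure for finding events. The protocol neither limits the comparison to events captured in the same way nor mentions the difference as a limitation.

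The causality judgement adds to this. Section 9(2) bases relatedness on timing, dose response, pharmacology and the effect of stopping or re-dosing. That can be judged as it happens for the 90, but would have to be reconstructed for the 30.

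At stake is the second study aim. A significant difference in total adverse effects could be a recording artefact, and a non-significant one could hide a real difference. The data as planned would not tell these apart.

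**Working it through.** The protocol gives no adverse-effect rate, power or sample-size derivation, so there is no figure of its own to reproduce. The calculation below is an illustration.

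**Inputs from the protocol:** n1 = 90 (combination), n2 = 30 (controls), chi-square or Fisher's exact test, P < 0.05 (sidedness not stated; two-sided taken).

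**Assumptions, not in the protocol:** the true risk p is the same in both groups, and a share c1 of affected patients is recorded in the combination group and c2 in the controls.

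**Formulas.** Recorded risks are p1 = c1·p and p2 = c2·p. For x and y recorded patients, the pooled rate is p̄ = (x + y)/120 and z = (x/90 − y/30) / √[p̄(1 − p̄)(1/90 + 1/30)]. The false-positive rate is the sum of Bin(x; 90, p1)·Bin(y; 30, p2) over all (x, y) with |z| > 1.96. Fisher's test uses the same sum with its own P < 0.05.

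**Hand check, p = 0.40, c1 = 1, c2 = 0.6.**
- p1 = 0.40, p2 = 0.24, spurious difference 0.16.
- p̄ = (36 + 7.2)/120 = 0.36; null SE = √(0.36 × 0.64 × 0.0444) = 0.101.
- Alternative SE = √(0.40 × 0.60/90 + 0.24 × 0.76/30) = 0.0935.
- Φ((0.16 − 1.96 × 0.101)/0.0935) = Φ(−0.41) ≈ 0.34, against 0.347 by exact enumeration.

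**Exact results at p = 0.40:**

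| Capture, combination | Capture, controls | Recorded risks | Chi-square | Fisher |
|---|---|---|---|---|
| 100% | 100% | 40% vs 40% | 4.9% | 3.5% |
| 100% | 80% | 40% vs 32% | 11.4% | 9.6% |
| 100% | 60% | 40% vs 24% | 34.7% | 31.6% |
| 100% | 50% | 40% vs 20% | 52.3% | 49.1% |
| 80% | 60% | 32% vs 24% | about 12% | about 11% |
| 70% | 60% | 28% vs 24% | about 6% | about 6% |

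**Sensitivity to the true risk** (chi-square, 100% vs 60% capture): 14% at p = 0.20, 23.5% at p = 0.30, 48.6% at p = 0.50. At p = 0.20 with 80% vs 60% capture it is about 7%.

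**What the table shows.** The error depends on the gap in capture and on the risk, neither of which the protocol lets anyone estimate. In the rows with lower control capture, most or nearly all false positives show the combination as worse. If capture were lower in the combination group, the false signals would favour it instead.

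**The case against.** The strongest reply is that the protocol never explicitly commits to testing adverse effects. In the Program Summary and Section 4 the P < 0.05 criterion attaches to laboratory tests, joint counts and DAS28. In those places and in Section 7, adverse effects stand apart and are only observed. The rule in Section 11 is generic and also serves other count data. This stands: a reader might infer a mandated significance test on adverse effects, but the text does not go that far. What remains is that Section 7 uses the side-by-side view to judge safety, and that the only rule given for count data would apply by default.

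A reader might also infer that control events come from charts and are under-recorded there. The protocol names no source, and the word for retrospective collection is attached to laboratory values, joint counts and DAS28. The dates nevertheless make control adverse-effect collection retrospective, except possibly the last weeks of a control who started late in 2021. Under-recording is an assumption.

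A third tempting reading is that the combination will look less safe than it is. That is not supported either. Exclusion criterion 4, worded for the combination, drops patients with serious reactions who do not complete. The related-events-only rule in Section 9(2) narrows what is recorded prospectively. Both would make the combination look better. For the same reason the 35% and 52% figures are not properties of the plan, since they need complete capture in the combination group.

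Finally, unequal ascertainment comes with historical controls, and that design is fixed. True, but which outcomes are compared, and whether a P value is attached, remains open.

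**Conclusion.** The point holds in a limited form. Adverse effects are ascertained prospectively in one group and in substance retrospectively in the other, and the protocol sets them side by side to judge safety. A difference in total rates may therefore reflect recording rather than treatment. The direction is undetermined.

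The size is unknown. With equal true risk of 40% and complete capture in the combination group, a nominal 5% chi-square test would reject in about 11% to 52% of studies as control capture falls from 80% to 50%. With a smaller gap (70% vs 60%) it would reject in about 6%. Fisher's exact test is slightly lower but does not remove the problem. All risk and capture values are assumptions.

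**What to change.** 1. In Sections 7 and 11, limit any between-group safety test to outcomes recorded alike in both groups: the listed laboratory values beyond limits fixed in advance, at the common weeks 0 to 24.
2. Add hospital admissions or drug stops only on two conditions. One identical record-abstraction procedure must be applied to both groups. Patients who stop or have serious reactions must also stay in the safety count of both groups and not be removed by exclusion criterion 4; otherwise identical abstraction cannot restore the missing events.
3. Report all other adverse effects descriptively by group, without a P value.
4. State how control events were ascertained: source, period searched, who judged relatedness, and whether the rule in Section 9(2) was applied to them.

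The cost is a change of wording and, if item 2 is taken up, one abstraction rule. No extra patients are needed. The downside is that there is no formal test of the total adverse-effect rate. The change addresses unequal recording only; other differences between a historical and a current group remain.

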
8. Start and end of the experiment

9.Data Security and Monitoring Program

(This paragraph cannot be deleted, if not, fill in none. According to the requirements of the Ministry of Health's Measures for Ethical Review of Biomedical Research Involving Human Beings (2016), all research projects are required to have a data security and monitoring plan, and this item is one of the criteria for the ethics committee to review the project, please describe it specifically according to the requirements.)

(1) Overview of data management methods

1.Data are traceable. All clinical trial data correspond to specific subjects and investigators, and all modifications to the data are recorded in detail to create a series of traceable verification traces.

2.Correctness of data. The correctness of data mainly includes the authenticity and accuracy of data, all clinical trial data reflect the actual situation of the study truthfully without any falsification, fiction and tampering; the accuracy is reflected in the verifiable data sources, i.e. CRF, study records and entered data should be consistent with the data obtained from the actual study.

3.Data completeness. Study data were collected completely for each subject, and missing data due to special reasons were stated as to why they were missing.

4.Logical reasonableness of the data. To determine whether the data are logically unreasonable from a clinical perspective.

5.Timeliness of data. The data are observed and completed in a timely manner at the specified time points in the clinical trial.

(2) Adverse events and serious adverse events are reported and collected.

Reporting principles: 1. Report only adverse events related to the study drug 2. Complete the Spontaneous Adverse Event Report Form for all related adverse events (serious and non-serious)

The following information should also be included to determine if the event is related, possibly related, or potentially related to the drug. Determination of event-drug relevance includes: 1. reasonable temporal sequence 2. dose-response relationship 3. pharmacology 4. discontinuation of dosing and/or positive re-dosing.

Classification of the severity of drug-related adverse events:

Mild	The symptoms do not alter the patient's normal function.
Moderate	The symptoms result in some degree of functional impairment, but are not damaging, uncomfortable, or embarrassing.
Severe	The symptoms are definitely detrimental to health, with significant

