①Case collection form: includes basic information of enrolled patients, related diseases, disease duration, treatment, and test data of related indicators for individual data analysis.

②Summary table: includes the patient's disease and related index examination data for overall data analysis.

2. Assessing the overall data situation

①Evaluate the integrity of each data source: timely recording of patient-related data to ensure data integrity.

②Evaluate the accuracy and consistency of aggregated data: randomly check whether the extracted data are consistent with those in the database to ensure data accuracy.

3. Data cleaning and collation

①Check for errors and outliers in the data that clearly defy common sense, and when found, first check that the same patient metadata are the same, then check how this data was collected, and finally how to assess whether it is an outlier from a technical point of view, by using relevant statistical indicators and methods such as setting upper and lower limits to deal with outliers.

②For special numbers, first mark "missing value", there is a perfect data dictionary to query the actual situation of this field, if not need to promptly communicate to confirm such issues

4. Data Collation

①Uniform formatting and naming rules for data

②Recoding of certain information to meet subsequent analysis needs

5. Data Visualization

Histograms, line graphs, scatter plots or heat maps are used to visualize the data of patient-related indicators to show the data results and trends more clearly, so that the study results can be presented more clearly.

6. Data Analysis

Complete the data and perform statistical analysis on those that meet the criteria

1) Frequency of data security and monitoring reports submitted to the ethics committee

The research in this project is a low-risk study, so an annual review frequency is used. Also, the principal investigator holds regular study meetings and notifies the ethics committee if there are changes in the risk/benefit ratio of the study.

10. Respect for ethical principles and related regulations

The study was conducted in strict compliance with international and domestic standards and norms,

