Glomerular filtration rate	pcs							
Swollen number of 28 joints	pcs							
DAS28-ESR score	score							
Ultrasound of joints								

14. Adverse reaction record form

No adverse events have occurred	 yes  no
Name of undesirable events	
Start date of occurrence	____ Year ____ month ____ day
Dosing time and dosage	____ year ____ month ____ day ____ mg
Severity*	 Mild  Moderate  Severe
Whether to take	 yes  no

measures	
Relationship to study drugs	 Definitely related  Likely related  Possibly related  Possibly unrelated  Definitely not related
Outcome of adverse events that occurred	 Still exists  Eased  No idea Relief Date _____ year _____ month _____ day
Whether the patient withdrew from the trial because of the adverse event	 yes  no

Severity*: mild (no treatment, no discontinuation), moderate (discontinuation, no treatment), severe (discontinuation, control treatment)

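### Section 9(2) limits adverse-event reporting to drug-related events, serious ones included, without saying how this fits the Section 14 form; severity also has two definitions

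*Protocol*

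**What the plan says.** Section 1 gives two purposes, efficacy and safety. Section 7 lists what is observed up to week 24, including "change in DAS28-ESR score and adverse effects", and sets no causality condition. It also looks at adverse effects between the combination group and the historical controls.

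Section 9(2) opens with an unqualified statement that adverse events and serious adverse events are both collected and reported. Two reporting principles follow. The first is "Report only adverse events related to the study drug". The second is "Complete the Spontaneous Adverse Event Report Form for all related adverse events (serious and non-serious"). The text then asks for the information needed to "determine if the event is related, possibly related, or potentially related to the drug". No unrelated level is named there.

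The Section 14 form offers definitely, likely and possibly related, and also "Possibly unrelated" and "Definitely not related".

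Severity appears twice. Section 9(2) grades drug-related events by their effect on the patient's function. The footnote to the Section 14 form grades by whether the drug was discontinued and whether the event was treated.

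**The concern.** This is a stated rule, so it is not a detail that could be waiting in a separate analysis plan. It makes reporting, including that of serious events, depend on a causality judgement made by investigators who know what the patient is taking. Section 2 of the protocol says that RA patients are already more prone to serious infection, cardiovascular disease and cancer. Events of that kind can be attributed to the underlying disease, and the rule then keeps them out of the reports.

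The rule also sits beside a form with boxes for unrelated events, and nothing explains which events go where. Two sites of practice, or two investigators in one department, could follow the text in good faith and record different sets of events. An event not captured prospectively may not be recoverable later.

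**Working it through.** No sample size, power or event count enters this point. The check sets the provisions side by side and counts definitions, not patients or events.

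**1. Causality levels**
- Section 9(2): related, possibly related, potentially related. That is 3 levels, all on the related side.
- Section 14: 3 related levels + 2 unrelated levels = 5. So 2 of 5 lie outside the reporting principles.

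**2. Two readings of how the forms relate**

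| | Section 14 records all events; 9(2) governs onward reporting | 9(2) governs collection as well as reporting |
|---|---|---|
| Non-serious event judged unrelated | recorded, not reported | may be neither recorded nor reported |
| Serious event judged unrelated | recorded, not reported | may be neither recorded nor reported |
| Unrelated boxes on the form | used | have no use |
| Opening sentence of 9(2) | collection all-cause; reporting narrowed | narrowed on both counts |

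The second row ends in non-reporting in both columns, so that part does not depend on the reading. Loss from the safety results arises only in the right-hand column.

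**3. Seriousness**

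The Section 14 fields are: none occurred, name, start date, dosing time and dosage, severity, measures taken, relationship, outcome, withdrawal. That is 9 fields, and 0 of 9 record seriousness. The Spontaneous Adverse Event Report Form may record it, but its fields are not shown and it is completed only for related events. A serious event judged unrelated therefore has no stated place where it would be marked as serious.

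**4. Severity**

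| Discontinued | Treated | Section 14 grade |
|---|---|---|
| no | no | mild |
| yes | no | moderate |
| yes | yes | severe |
| no | yes | none |

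One of the 4 combinations has no grade. Among those that do, the two scales can disagree:
- Function unchanged, drug discontinued, no treatment: mild under Section 9(2), moderate under Section 14.
- Some functional impairment, drug continued, no treatment: moderate under Section 9(2), mild under Section 14.

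**The case against.** The best defence is that the protocol describes a record-then-filter process. Section 9(2) opens without a causality limit. The restriction comes afterwards, under a label about reporting, and its second item concerns one named form. Causality cannot be assessed until an event has been noted. The unrelated boxes on the Section 14 form have a purpose only if unrelated events are entered there. Section 7 applies no causality filter, and Section 9(1) says "Study data were collected completely for each subject". The study is also observational with no imposed treatment, and nothing in the document requires all-cause reporting.

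Much of this stands. It makes the lenient reading plausible, so loss from the recorded data is possible but not shown. It does not remove the reporting gap for serious events judged unrelated, and no sentence actually orders capture regardless of causality. The observational label does not help, because safety is a stated purpose.

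A reader might go further in two ways that the document does not support:
- The case collection form in Section 9 ("includes basic information of enrolled patients, related diseases, disease duration, treatment, and test data of related indicators for individual data analysis") does not name adverse events, which could suggest they are not collected. It does not name DAS28, joint counts or ultrasound either. Sections 13 and 14 are the itemised forms, so the omission shows nothing.
- The notice to the ethics committee of a changed risk/benefit ratio could be thought to rest on the filtered reports. Section 9 does not say what it rests on, and it also provides for regular study meetings and departmental risk monitoring.

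**Conclusion.** The point holds in a limited form and should be fixed. On either reading, a serious event judged unrelated is not reported under Section 9(2), and the Section 14 form cannot identify it as serious. On the stricter reading only, events judged unrelated can also fall out of the safety results, which would then depend on unblinded attribution. It would be too strong to say that the protocol discards such events: the text leaves that unresolved, and it gives no basis for estimating how many would be affected.

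The severity conflict is real but secondary. No passage analyses the grades, so it changes how an event is described and not whether it is counted.

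The conclusion assumes that no other instruction on capturing events exists outside the document, for example in a form guide, and that investigators know the treatment, since patients enter according to the treatment they receive and no blinding is described.

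**What to change.** Replace reporting principles 1 and 2 in Section 9(2) with a rule on these lines: all adverse events through week 24 are recorded on the Section 14 form regardless of causality, with causality and seriousness stated for each; the safety results use all recorded events; all serious adverse events are reported regardless of causality. The Spontaneous Adverse Event Report Form can stay for related events, provided the text says so. Add a serious yes/no field to the Section 14 form.

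Reconcile the two severity definitions into one that gives every event a grade, and use it in both places. The basis for grading is for the investigators to choose.

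Describe the adverse-event comparison with the 30 historical controls as limited by different ascertainment. Their data are collected retrospectively, and all-cause recording in the prospective group does not correct that. It may widen the gap.

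The cost is a short replacement text, one severity definition and one form field. The downside is somewhat more recording for 90 patients and higher reported event rates.
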